## ROKHYT TRIAL PROTOCOL

**The specific aims of this protocol** are to:

1. Develop and pre-test the intervention text messages.
2. Pilot the enrollment, consent, randomization, and data collection procedures at baseline and 3, 6, and 12 months and document participation and completion rates in a randomized pilot study of N=70 per group.
3. Obtain demographic data on potentially eligible participants using an on-line questionnaire.
4. Pilot test the text messaging intervention and document blood pressure control rate in response to the intervention.
5. Pilot test secure data transfer and other data coordinating center (DCC) functions.

The following metrics will be used to decide whether to proceed with a larger trial: **Aim 1**. Successful piloting of text messages including tailored features, based on positive feedback from pilot subjects. **Aim 2**. Successful enrollment, consent, and randomization of N=70/group. **Aim 3**. Completion of >80% of all data fields. **Aim 4**. Completion of 12-month follow-up by >80% of those randomized; positive signal of intervention effect. **Aim 5**. Successful and secure transfer of all pilot data from higi to the DCC.

The overall goal is to provide pilot data to support an application to conduct a fully powered randomized controlled trial.

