### **Phases of the project**

There are three phases to the project, as follows.

- A. **Pretesting of Text Messages.** We will use formative interviews conducted by telephone to iteratively test the text messages and videos.
- B. **Vanguard.** We will run 10 vanguard or pilot subjects (randomized 7 to intervention and 3 to control) through a compressed 3-month protocol involving the invitation, consent, and baseline data collection, and follow-up data collection at 1, 2, and 3 months (blood pressure only at 1 and 2 months, blood pressure and exit questionnaire at 3 months).
- C. **Trial.** We will conduct the pilot trial (N=70 in each of the two randomized groups).

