- \$100 at 12-month blood pressure check and final survey. All higi communications are available in English or Spanish as selected by the individual. **Eligibility** criteria are shown in table 3. **Consent** will be obtained electronically, also in English or Spanish. **Randomization** will be stratified by sex, age (18-55, 56-85 years), and region of the country (northeast, southeast, north central/west, south central/west), assigned 1:1, and performed by the DCC using the web-based trial management system. Participants will receive email informing them that they have been enrolled and which group has been assigned. **Data collection** for Aim 3 will be accomplished using an electronic form with multiple-choice or numeric response sets on the secure web portal, to be completed as part of the consent process. We will obtain BP measurements at the kiosk at time of enrollment and at 3, 6, and 12 months post randomization. For follow-up measurements, subjects will receive email messages prompting them that it is time to obtain a study BP measurement at a kiosk along with instructions about how to take the BP, specifically to take all of their usual medications the day they take the BP, to log in at the kiosk using their account identifier (email address) when they take the BP, and to take the BP three times at intervals of about one minute. Subjects will receive up to \$200 in Bank of America pay card by mail when completing each blood pressure check points. **Participation rate** will be calculated as the proportion of those invited to participate and eligible who consent and complete the baseline questionnaire and BP measurement. **Completion rate** will be calculated as the proportion of those randomized who complete the 12-month follow-up BP measurement. We do not propose to replace randomized individuals who die, drop out, or are lost to follow-up in either the pilot or the full scale study.

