Title: Retail Outlet Health Kiosk Hypertension Trial (ROKHyT)

Registration#: NCT03515681

Protocol Version Date: 15APR2019

Statistical Analysis Plan

The overall goal of the R34 pilot grant is to develop pilot data for an application for a fully powered trial. The intervention using interactive text messaging will be compared to current information provided in the context of higi installation (usual care). The primary endpoint will be hypertension control defined as < 149/90 mmHg at 12 months post randomization. Measurements will also be obtained at 3- and 6-months post randomization.

The specific aims are shown in table 1.

Table 1. Specific Aims
1. Develop and pre-test the intervention text messages
2. Pilot the enrollment, consent, randomization, and data collection procedures at baseline and 3, 6, and 12 months and document participation and completion rates in a randomized pilot study of N=70 per group.
3. Obtain demographic data on potentially eligible participants using an on-line questionnaire.
4. Pilot test the text messaging intervention and document blood pressure control rate in response to the intervention.
5. Pilot test secure data transfer and other data coordinating center (DCC) functions.

Aim 1. No statistical analysis.

Aim 2. The numbers enrolled, consented, and randomized will be tabulated.

Aim 3. Demographic characteristics will be tabulated.

Aim 4. The proportion in each group (intervention and control) achieving blood pressure control at 12 months will be tabulated and the difference between these proportions will be calculated. Control will be defined as systolic blood pressure <140 mmHg and diastolic blood pressure <90 mmHg. A Mantel-Hanzel relative risk with adjustment for stratification will be calculated comparing the two groups. In addition, the proportions achieving blood pressure control at 3-months and 6-months follow-up will also be tabulated. Formal statistical testing will not be done because the pilot study is not powered for hypothesis testing.

Aim 5. No statistical analysis.

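### The 12-month risk difference is unadjusted while the relative risk is adjusted for the randomization strata; a stratified difference should be added and used to read the positive signal

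*SAP*

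**What the plan says.** SAP Aim 4 tabulates the proportion controlled in each group at 12 months and states that "the difference between these proportions will be calculated". It mentions no adjustment, so the plain reading is a crude difference. The SAP then plans a second measure: "A Mantel-Hanzel relative risk with adjustment for stratification will be calculated comparing the two groups". At 3 and 6 months it only tabulates proportions. It rules out formal testing and plans no standard error or interval.

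The protocol (Aim 2, Randomization) has allocation "stratified by sex, age (18-55, 56-85 years), and region of the country (northeast, southeast, north central/west, south central/west), assigned 1:1". It does not mention blocking or any other way of keeping the arms balanced within strata. There are 70 people per group, and those lost are not replaced. The decision metrics at the start of the protocol ask for more than 80% completion at 12 months and a "positive signal of intervention effect". Neither document says which effect measure defines that signal, or how strata left with one arm are handled.

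**The concern.** The plan adjusts one of its two 12-month effect measures for the randomization strata and leaves the other crude. Stratified allocation keeps the two close only while the arms stay balanced within strata. With 16 small strata and some loss to follow-up, that balance is partly lost.

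The crude difference then carries any chance or loss-driven imbalance in sex, age and region, while the relative risk does not. Strata left with one arm drop out of the relative risk but stay in the crude difference. The positive-signal criterion has no threshold, no test and no named measure. If it is read as a direction, the plan leaves open which of two possibly different directions counts.

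**Working it through.** **Inputs from the documents.** 140 people; 2 (sex) × 2 (age) × 4 (region) = 16 strata; 140/16 = 8.75 per stratum. At 80% completion, 112/16 = 7. The plan gives no figure for the effect measures, so there is none to reproduce.

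**Formulas.** In stratum i, let a and b be the numbers controlled in intervention and usual care, n1 and n0 the numbers measured, and N = n1 + n0.
- Crude difference = Σa/Σn1 − Σb/Σn0
- Mantel-Haenszel relative risk = Σ(a·n0/N) / Σ(b·n1/N)
- Mantel-Haenszel difference = [Σ(a·n0/N) − Σ(b·n1/N)] / Σ(n1·n0/N)

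The stratified difference has as its numerator the relative risk's numerator minus its denominator. It is therefore positive exactly when the relative risk exceeds 1, and these two cannot conflict.

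**Step 1: exact balance.** If n1 = n0 in every stratum, the relative risk reduces to Σa/Σb, the crude ratio. In 20,000 random balanced tables the largest discrepancy was 0. A conflict needs residual imbalance.

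**Step 2: how much imbalance.** Take two strata with 60% and 30% control in usual care, 70 per arm. Intervention has 35 + k in the better stratum and 35 − k in the other; usual care has the reverse. Then crude difference = true difference + (2k/70) × 0.30, while the Mantel-Haenszel difference equals the true one.

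| k | True difference | Crude difference | MH relative risk |
|---|---|---|---|
| 2 | −1 point | −1.0 + 1.7 = +0.7 | 0.88/0.90 = 0.978 |
| 3 | −2 points | −2.0 + 2.6 = +0.6 | 0.86/0.90 = 0.956 |
| 6 | −5 points | −5.0 + 5.1 = +0.1 | 0.80/0.90 = 0.889 |

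Small imbalances reverse only small effects.

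**Step 3: 16 strata, simulated.** Assumptions not in the documents: about 40% control in usual care, strata moderately or strongly prognostic on the logit scale, regions of unequal size, permuted blocks of 4. The table gives the share of trials in which the crude difference and the relative risk point in opposite directions (6,000 runs per setting).

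| True difference | No loss | 20% loss |
|---|---|---|
| 0 | 3.7–5.0% | 7.4–9.4% |
| 10 points | 1.9–2.2% | 4.1–4.5% |
| 15 points | 0.6–0.9% | 1.8–2.0% |

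Other stratum assumptions with 20% loss widen these ranges to 6–11% at no effect and 3.5–7% at about 8 to 10 points. The crude and stratified differences are then 1.6 to 2.4 points apart on average (95th percentile 4 to 6). With no balancing within strata, conflict at no effect is 12–17%.

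**Step 4: size of the conflicts.** With blocks of 4, the median absolute crude difference in conflicting trials is 0.4 to 1.7 points, and the 95th percentile is at most 4.5. The crude and adjusted log relative risks correlate at 0.96 to 0.99. For scale, with 40% control and 56 measured per arm, the SE of the crude difference is √(0.4 × 0.6 × 2/56) = 0.093, or 9.3 points.

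**Step 5: loss that differs by arm and stratum.** In simulations of such loss, the crude difference was biased by about 1.6 to 3.1 points and the Mantel-Haenszel difference by under 0.3. Step 2 shows why: at k = 2 the arms' shares in the better stratum differ by 4/70 = 5.7 points, which alone shifts the crude difference by 5.7 × 0.30 = 1.7 points.

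**Step 6: cost.** If the strata do not predict control, the stratified difference has an SD of 0.0957 against 0.0933, a ratio of 1.026. With blocks of 4, strata left with one arm remove 0.1 to 1.2 participants on average (0.6 to 1.2 at 20% loss).

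**The case against.** Raw proportions with a raw difference, beside one adjusted measure, are ordinary descriptive practice. The SAP rules out testing, and the protocol calls the main approach data summarization. That stands, and it is why the crude difference should stay.

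The conflicts are mostly sign noise around zero. In one simulation, opposite signs with both estimates beyond 2 points occurred in at most 0.7% of trials, and in conflicting trials neither estimate exceeded 0.9 of the crude SE. Strata with no prognostic value still gave 5.8% conflict at no effect and 20% loss, so much of the disagreement is not confounding by strata. This stands as to size. It does not settle a criterion without a threshold, which is most sensitive to direction when estimates are near zero.

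Precision does not improve: with strong strata and 20% loss the SDs were 0.0870 (crude) and 0.0866 (stratified) at no effect. That also stands.

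Naming the planned relative risk as the deciding measure would settle direction too. That is true, but it would leave the only absolute measure exposed to imbalance.

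Three stronger readings are tempting but unsupported:
- A reader might infer that the two measures will often contradict each other. Stratified allocation works against this, and conflict is uncommon away from the null.
- A reader might infer that the plan's error bars are too wide. The SAP plans none.
- A reader might infer that the crude difference will size the full trial. The documents do not say so; the pilot is described as 10% of a trial already planned.

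**Conclusion.** The inconsistency is real and modest. The two 12-month measures adjust differently and, where a stratum is left with one arm, rest on slightly different participants. Under blocks of 4 and 20% loss they differ by about 2 points on average and occasionally in sign, almost only when both are near zero. That is small against an SE of about 9 points.

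Two benefits justify the change: the absolute and relative measures would always agree in direction, and the absolute measure would be protected when loss differs by arm and stratum. That protection does not extend to loss that depends on blood pressure itself within an arm and stratum.

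The conflict rates and the bias of 1.6 to 3.1 points rest on assumed control rates, stratum effects, block size and loss patterns that the documents do not give. The 20% loss is the limit of the completion target, not a forecast. The algebra in Steps 1 and 2 needs none of the simulation assumptions.

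**What to change.** In SAP Aim 4:
- Keep the crude proportions and their difference, labelled as descriptive.
- Add the Mantel-Haenszel risk difference over the sex × age × region strata, with a 95% CI (Sato variance). The interval describes uncertainty and is compatible with the decision not to test.
- State that the protocol's positive-signal criterion is read from this stratified estimate, whose direction always matches the planned relative risk.
- State how strata left with one arm are handled, and report how many participants they contain.

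No change is needed at 3 and 6 months, where only proportions are planned; a stratified difference there would be an optional addition.

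The cost is a few sentences in the SAP and about one line of code. Statistically, it is an SD up to about 2 to 3% larger if the strata are not prognostic, and about one participant on average dropped from the stratified estimate. The tabulated proportions will not subtract exactly to the stratified difference, so both should be shown and labelled.
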